Recruitment. Given the inclusion criteria and site volume for the pilot, we expect to recruit 15 youth per arm (intervention and attention control) session for a total of 3 cohorts of 15 in each arm or 6 total groups. Based on what we've learned from previous studies with YEH, we will recruit 90 youth to deliver the intervention or control to at least 60 youth. Youth will be recruited primarily from Covenant House Texas (CHT), and homeless shelters and drop-in centers if additional recruitment sites are needed, to participate in the pilot. Youth who are eligible and enroll in the pilot study will complete a baseline survey, attend 5 90 minute sessions, complete very brief pre-post session surveys, as well as follow-up surveys immediately post-intervention and at 3 months post-intervention. Approximately 22% (n=20) of the pilot study participants will be recruited to also participate in a post-intervention exit interview. Participants will have the phone for the duration of the study. The intervention is informed by the Risk Amplification Model (RAM) and the Minority Stress Model (MSTM) and will be fully developed in Years 1-2 using a systematic intervention development process; Plan, Do, Study, and Act. In order to ascertain the feasibility and acceptability of the intervention (Aim 3), we will obtain participant feedback via exit interviews as well as quantitative implementation indicators (e.g., refusal rate, completion rates, and survey measures).

Inclusion/Exclusion of Service Providers. Key Informant Interview participants (n=12) and Expert Advisory Panel service provider members (EAP, n=8) will be health and social service providers for YEH recruited from local shelters (i.e., resident advisors, in-take specialists), drop-in centers (i.e., social workers, case managers), homeless healthcare clinics (i.e., nurses, mental health counselors, patient navigators), and the Homeless Youth Network (a network of YEH providers, of which [name] is an active member). Providers will be considered eligible if they are currently providing health or social services to YEH and are interested in participating in an interview or as a member of the Expert Advisory Panel. For those providers interested in the EAP, they will be considered eligible if they anticipate being able to meet for the regularly scheduled meetings at least 75% of the time.

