session participation, mindfulness skills practice, measures completion, and overall experience with the intervention and the study. While the exit interview guide will be finalized during YR-1 with the assistance of the HYWG, we anticipate querying the participants about: 1) what the participant thought of the number and type of questions asked in the baseline, pre-post session, and initial follow-up survey, 2) thoughts on the intervention sessions (e.g., content, length, delivery mode, frequency/spacing, perceived impact), and 3) any other comments about the intervention or study procedures including a comparative analysis¹⁸⁰ of the commercially available mindfulness apps. Participants will receive an additional \$10 gift card for a local restaurant or grocery store for completing the exit interview.

Table 3. Feasibility and Acceptability Benchmarks

Construct	Measure	Benchmarks
Recruitment feasibility	# screened & enrolled/mo; time delay from screening to enrollment; average time to enroll sufficient class size; appropriateness of exclusion criteria screening process	Enroll 50% of screened and eligible participants; <2-week delay from screening to enrollment; <2 weeks to enroll sufficient class size; <5% inappropriate exclusion/inclusion
Retention feasibility	3- and 6-mo follow-up survey completion; compare intervention vs. control group	At least 50% retained at 3 and 6-mo; <15% group retention differential
Treatment adherence	Attend all sessions; perform the intervention; complete study measures	At least 50% of participants in each cohort will attend at least 3 of 5 scheduled group sessions ^{108,164}
Treatment delivery fidelity	Session delivery fidelity checklist	At least 70% of each session content is completed
Completeness of assessment data	Data from surveys, focus groups, and key informant interview are complete and intact	Less than 50% data loss or incompleteness
Acceptability	Credibility/expectancy questionnaire ¹⁸¹	Average score of >30

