Drs. [name], [name], [name], and [name] will meet every 2-4 weeks (by phone and/or in person) to monitor study progress. Any adverse reactions noted by any of the team members will be immediately reported to the principal investigator, the UTHealth IRB, Data Safety and Monitoring Board, and NCCIH. One focus of investigator meetings will be on developing strategies to prevent adverse reactions and to better monitor the research staff and data integrity. Accrual data will be reviewed by the UTHealth IRB. The study team will make amendments to the protocol should accrual fall below 25% of the target, or should drop-outs exceed the projected 15-20%.

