Role of NIH. Summaries of the protocol and design, status of intervention group, and data collection procedures, summary of subject contacts, discussion of any adverse reactions or any potential adverse reactions, status of data entry and verification, a summary of any descriptive statistics to date, and the recommendations of the monitoring board will be included in each annual report to NIH. In addition, should any adverse reaction occur or should the monitoring board recommend early termination of the study, the information will be immediately reported to the program officer at NCCIH.

Statistics

Fifty six YEH will participate in the focus groups during the first 2 years of the study to Tailor .b and finalize the attention control condition. Sixty YEH will participate in the pilot RCT.

Sample Size for Pilot RCT. We will recruit 90 YEH with equal randomization into the intervention and attention control arms to reach the target of 60 YEH completing the intervention and control conditions. The sample size is based on practical considerations regarding the number of participants needed to assess feasibility and acceptability outcomes and not on the performance of inferential statistical analyses. However, a final sample size of 60 youth completing the pilot will have 80% power to detect a medium effect size of 0.74 for stress response.¹⁸²

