Data Management and Statistical Analysis Plan. To align with the R34, we will not conduct inferential statistical analyses. The analyses goal is to examine study feasibility and acceptability, determine effectiveness of recruitment and randomization strategies, follow-up and retention protocols, and preliminary assessment of outcome measures using both quantitative and qualitative methods (See Table 3). In summary, for the quantitative analyses, frequencies and percentages will be calculated to determine the recruitment, retention, attendance, and data collection rates (See Table 3). While we do not anticipate missing data based on the low rate of missingness in our previous work using similar surveys and data collection methods, we will assess for and calculate the rates of missing and incomplete data to inform future studies. Means and standard deviations will be used to summarize changes in the outcome variables over the three time points (e.g., baseline, immediate post-intervention, and at 3- and 6-months). Estimation of effect sizes due to the intervention will involve the use of one-way repeated measures analysis of variance to provide the effect size R² for each proposed outcome variable.

For the qualitative analyses, we will analyze the data from FGDs, key informant, and exit interviews using thematic content analysis.^{174,183} Audio files will be transcribed and validated against the written transcriptions. For the initial set of 2 FGDs and 5 interviews, the qualitatively trained RA will review the text for content and identify 5-10 themes. Next, we will develop a codebook through preliminary discussions of themes and team coding among the study team and refine the codebook iteratively with the HYWG and EAP to form a final set of codes. Then, two investigative team raters (Drs. [name] and [name]) will independently categorize passages until excellent interrater reliability (Cohen's kappa (k) = .85) is achieved. A thematic content analysis will be conducted to look for common themes present across the entire sample. The investigative team will discuss emerging themes and subthemes with the HYWG and EAP to generate the final results. ATLAS.ti will be used to manage the data, organize codes, and exemplar quotes. The team will meet to review coded data and discuss the meaning of the themes

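### The plan anticipates no missing data and takes intervention effect sizes from a one-way repeated measures ANOVA, although its own figures are 15-20% drop-out projected, one third not completing, and up to 50% loss tolerated

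*Combined protocol and SAP*

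**What the plan says.** The Data Management and Statistical Analysis Plan states "While we do not anticipate missing data based on the low rate of missingness in our previous work". It commits to calculating the rates of missing and incomplete data, but names no analysis set, no method for missing waves and no sensitivity analysis. Effect sizes attributed to the intervention are to come from "one-way repeated measures analysis of variance to provide the effect size" R² for each outcome. The same section rules out inferential analysis. It speaks of three time points but lists four.

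The protocol gives three other figures for loss:

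- **Projected drop-out.** Role of the PI and Investigative Team provides for amendments "should drop-outs exceed the projected 15-20" per cent.
- **Planned non-completion.** Sample Size for Pilot RCT sets this out: "We will recruit 90 YEH with equal randomization into the intervention and attention control arms to reach the target of 60 YEH completing". Completion here refers to the assigned condition. The Recruitment text under Study Population agrees: "we will recruit 90 youth to deliver the intervention or control to at least 60 youth". Intervention Delivery plans 15 recruited per group for an average final size of 10.
- **Benchmark floor.** Table 3 sets "At least 50% retained at 3 and 6-mo" as success, and separately accepts anything under 50% data loss.

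**The concern.** None of these figures fits an expectation of no missing data, and they do not agree with one another. The named method makes the conflict matter in two ways.

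First, conventional repeated measures ANOVA needs a value at every wave, so a youth who misses one survey contributes nothing. Second, a one-way model, read literally, has time as its only factor. Its R² measures how much scores move over time. It does not estimate the contrast between tailored .b and the attention control.

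General Information and Objectives both say that the pilot will inform the sample size of the full trial. An effect size that omits the arm contrast, or comes only from youth who stayed, is a poor input for that purpose whether or not a hypothesis test is done here.

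**Working it through.** **1. The plan's own figure.** Inputs from Sample Size for Pilot RCT: 60 completers, equal allocation (30 per arm), standardised effect 0.74, power 80%. Alpha is not stated, so two-sided 0.05 is assumed.

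- Normal approximation: 0.74 × √(30/2) − 1.96 = 2.866 − 1.96 = 0.906, and Φ(0.906) = 81.8%.
- Noncentral t: 80.5%.

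The stated 80% reproduces. It applies to 60 of 90, so that section already allows for a loss of 30/90 = 33.3%.

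**2. Youth left for a complete-case analysis.** If the same youth are missing at every wave, the number left is 90 × (1 − loss):

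- 15-20%: 90 × 0.85 = 76.5 and 90 × 0.80 = 72
- one third: 90 × 2/3 = 60
- one half: 90 × 0.5 = 45

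Fewer remain if different youth are missing at different waves. At 50% retention with independent losses at 3 and 6 months, 90 × 0.5 × 0.5 = 22.5, about 22. Independence is an assumption; the plan does not state it. Loss at the immediate post-intervention survey would reduce any of these counts further.

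**3. Precision for the arm difference.** With n per arm and d = 0.74, the approximate 95% half-width is 1.96 × √(2/n + d²/(4n)). For n = 30: 1.96 × √(0.0667 + 0.0046) = 0.52. Power and smallest detectable effect use the t distribution, two-sided 0.05.

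| Source of figure | Left of 90 | Smallest d at 80% power | Power at d = 0.74 | 95% CI half-width |
|---|---|---|---|---|
| No loss | 90 | 0.60 | 93.5% | 0.43 |
| 15-20% projected | 76-72 | 0.65-0.67 | 89-87% | 0.46-0.48 |
| One third planned | 60 | 0.74 | 80.5% | 0.52 |
| One half (floor) | 45 | 0.855 | 68% | 0.60 |

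**4. What a time-only R² measures.** Illustration on assumed values: 60 youth, four waves, total variance 1, within-person variance 0.4, and both arms changing equally by 0.4 SD after baseline, so that the intervention has no effect.

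- Wave means 0, −0.4, −0.4, −0.4 have mean −0.3 and squared deviations 0.09 + 3 × 0.01 = 0.12.
- Expected time sum of squares: 60 × 0.12 + 3 × 0.4 = 8.4.
- Expected residual sum of squares: 59 × 3 × 0.4 = 70.8.
- R² ≈ 8.4/(8.4 + 70.8) = 0.106. A simulation gave the same value, 0.106.

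R² is about 0.11 with no intervention effect at all.

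**5. Can selection matter?** Illustrative simulation with an assumed true d of 0.30 and 45 per arm, comparing retained youth between arms at the last wave. When loss is unrelated to outcome, the completer estimate stays near 0.30. When intervention-arm youth with worse outcomes leave more often, it averages 0.37-0.45 at 20% loss, 0.42-0.52 at one third and 0.47-0.62 at one half. These inputs are not from the documents. They show only that the size of any bias depends on why youth are lost.

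**The case against.** The quoted sentence refers to earlier work with similar surveys and collection methods, so it may mean skipped items and not lost follow-up. The plan also commits to measuring missingness and to comparing retention by arm, describes the outcome assessment as preliminary, and plans no inference. The feasibility endpoints do not depend on the ANOVA. All of this stands and limits the reach of the point. It does not supply a method for missing waves: on the item-level reading, the plan is silent on them. Complete-case analysis is an inference from the method named, but nothing in the section points to another approach.

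A reader might go further in four ways that the documents do not support:

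- **That the plan expects a third to a half of youth to be lost.** The 50% is the minimum that passes a benchmark. The one third is mainly non-completion of the conditions, although the sample size paragraph also speaks of completing the pilot, so the term is ambiguous. The only figure labelled as projected drop-out is 15-20%. Youth who leave the shelter may continue, with tracking, transport vouchers and off-site surveys.
- **That the effect sizes will be biased.** That depends on why youth are lost, which is unknown.
- **That the standard deviations would come only from completers.** Means and standard deviations are a separate descriptive summary, and nothing restricts them to youth with every wave.
- **That independent losses at each wave can be applied to the other two figures.** Squaring two thirds or 80% gives 40 or 58 youth, but those figures describe overall completion or drop-out, not loss per wave.

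**Conclusion.** The point holds in this form: the statement about missing data conflicts with every attrition figure in the protocol, and the named method is poorly suited to estimating an intervention effect when waves are missing. If the same youth are lost throughout, the complete-case set is 72-76, 60 or 45 of 90 under the projected, planned and tolerated figures. The half-width for a standardised difference of 0.74 then rises from 0.43 with no loss to between 0.46 and 0.60. These sizes assume a two-arm comparison at two-sided 0.05 and conventional complete-case handling.

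The loss of precision follows from dropping partial data. Bias is a risk only. The protocol gives some reason to take it seriously, since it describes these youth as transient. In addition, the exclusion criteria under Study Population have participants with significant symptoms removed from the study, whereas the corresponding text in Study Procedures and in Adverse Event Reporting describes consultation with the DSMB without mentioning removal. Those passages need reconciling, because removal would tie loss directly to the outcomes.

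The missing arm term depends on reading one-way literally. If arm was meant to be included, the plan should say so.

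**What to change.** 1. Reconcile the 15-20%, 33% and 50% figures. Say which is expected survey loss, which is non-completion of sessions and which is a benchmark floor. Remove the statement that missing data are not anticipated, or limit it to item-level gaps. State the number of waves consistently: the analysis section counts three but lists four, and some sections stop follow-up at 3 months.
2. Replace the one-way ANOVA with a linear mixed model on all randomised youth, using every available wave. Enrollment is currently defined as including at least one lesson after assignment, which could exclude randomised youth, so the analysis set should be spelled out. Treat baseline either as one of the outcome waves (arm, time and arm-by-time, with baseline means constrained equal between arms) or as a covariate, but not both. Report the standardised arm difference at each follow-up with a 95% CI, described as preliminary.
3. Tabulate baseline characteristics of retained and lost youth by arm. Add a simple sensitivity analysis, because the mixed model assumes that data are missing at random and need not remove selection that breaks that assumption.

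The cost is SAP wording and slightly more analysis work. No additional participants or data collection are needed.

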Purpose. The purpose of this pilot study is to examine intervention feasibility and acceptability and determine effective recruitment and retention strategies, randomization processes, participant tracking and follow-up procedures, retention benchmarks, and evaluate the feasibility of outcome measures. To this end, we will conduct this feasibility trial using a two-group randomized attention control trial design.

Intervention Delivery. Drs. [name] and [name] are certified teachers of existing youth-focused MBI curricula, *.b*⁸⁹ ([name], [name]), and *MBSR-T*¹⁰⁸ ([name]), and will work with the interventionist if issues arise during intervention delivery. Additionally a fidelity checklist will be made to assess the delivery of the tailored *.b*. While the session length, group size, and session spacing will be informed by the PDSA work with the HYWG and finalized in the formative phase, we describe our estimates below. We anticipate between 4 and 5 intervention sessions that will last between 60-90 minutes. Each cohort will include approximately 10-15 youth. Based on attendance at our recent pilot *.b* program, we plan to recruit 15 youth to have an average final group size of 10 youth depending on HYWG preferences and PDSA data. We anticipate having 6 cohorts of youth (3 intervention and 3 attention control). Each session will likely include brief didactic presentations, videos, and mindfulness practice followed by inquiry. We anticipate that sessions will take place twice a week. Sessions will be held on site at the CHT shelter in a quiet, designated learning space to ease access to sessions for the participants and to assure access to shelter staff (e.g., social workers and case managers) and services (e.g., food and shelter). CHT has onsite, weekday clinical and mental health care and established protocols for accessing needed resources 24/7. Selection criteria for the interventionist include maintaining a personal mindfulness

practice for at least two years, trained in .b, and prior experience working with high-risk youth. The interventionist will receive additional training in Trauma-Informed Care as well as study procedures.

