Attention Control Condition. Working with the HYWG in YR-1, we will modify the health education program Healthy Topics (HT) adapted from the Glencoe Health Curriculum (McGraw Hill) from its current eight-session format to match the intervention condition and serve as an active control condition. [name] (Co-I) previous RCTs have shown that HT is an effective control condition for MBI.^{94,95,125,126} HT will be matched for session frequency and length, group size, location and timing, didactic instruction, and group discussion. HT is an appropriate attention control since it provides beneficial health information and is likely to attract youth interested in their health. Additionally, the active control condition controls for the effect of meeting with a positive adult instructor and peer group experience, learning new material, attention, and time. HT participants receive no training in MBI or meditation. Topics covered may include physical activity, nutrition, managing weight, understanding adolescence, personal care, avoiding tobacco, alcohol, and drugs though this will be finalized in YR-1 with the HYWG and advisory panel. The HT program will be led by a positive adult instructor with training in health education or a related field and experience working with YEH.

Participant Incentive. Participants in the pilot study will receive food, hygiene items, and a \$10 gift card for attending each session and \$15 for the baseline and immediate post-intervention surveys. To facilitate retention in the study, participants will receive \$20 for the 3- and 6-month follow-up surveys. CHT has bus passes available for all YEH who are in need of public transportation. Rather than receiving compensation for attending the sessions, youth will receive food and toiletries as needed, current practice in the shelter for attending life skills courses.

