Enrollment and Data Collection Procedures. The RC and RA will recruit and enroll all participants. Once consented, the youth will take the baseline survey and receive their group assignment from the RC. A computerized randomization generator will be used. The RA will be blinded to group assignment and will conduct all data collection. For the purpose of this study, enrollment will be defined as completing consent, baseline survey, and at least one lesson of the intervention or control condition. Surveys will be completed by participants on iPads using REDCap. Participants will enter response data directly into the tablet so their answers will be private. In the case of electronic device failure, we will use back-up iPads and paper surveys and the RA will enter the responses into REDCap within 24 hours. We will use unique study IDs in the place of names to protect participant confidentiality. **Baseline and Follow-up Surveys.** Participating youth will complete surveys at baseline, immediate post-intervention, and at 3- and 6-months post-intervention. Surveys will take approximately 30 minutes to complete and will include items to measure mindfulness, perceived stress, emotion regulation, impulsivity, and mental health symptoms (see Table 2 for example measures and psychometric properties) and youth risk behaviors. We will also pilot self-report and app use to determine the most effective way to measure use of commercially available mindfulness apps. Data usage information will be gathered from mediation app on participants' phone. **Pre- and Post-Session Surveys.** Very brief pre- and post-session brief surveys will capture real-time stress, emotion regulation, positive and negative affect, mindfulness, impulsivity, and session feedback (post-session only) including likability of session content, delivery format, length, and delivery timeframe. These surveys will take approximately 5 minutes to complete prior to and immediately after each session. **Exit Interviews.** The RC will conduct individual or group exit interviews with 20 youth from the pilot study participants that will be audio-recorded and take about 30-45 minutes. We will randomly select participants from each of the 4-6 intervention cohorts to have equal representation by gender identity, age, and study group. We will elicit participant feedback on study procedures, intervention acceptability, delivery methods and strategies, barriers and facilitators of

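### Outcome effect sizes are to come from a one-way repeated measures ANOVA, whose R² describes change over visits and not .b against the attention control

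*Combined protocol and SAP*

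**What the plan says.** The Purpose paragraph under Specific Aim 3 sets the design: "we will conduct this feasibility trial using a two-group randomized attention control trial design". Sample Size for Pilot RCT specifies equal randomisation of 90 youth, with 60 expected to complete. The Attention Control Condition paragraph explains that the control programme "controls for the effect of meeting with a positive adult instructor and peer group experience, learning new material, attention, and time".

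The outcome scales are covered by two sentences of the Data Management and Statistical Analysis Plan. The first is descriptive: "Means and standard deviations will be used to summarize changes in the outcome variables over the three time points". It does not say whether the summaries are by arm, and it refers to three time points but lists four. The second is: "Estimation of effect sizes due to the intervention will involve the use of one-way repeated measures analysis of variance", which is to yield an R² per outcome. R² is not defined. No arm factor, arm-by-visit term, between-arm difference or baseline adjustment is mentioned, and it is not stated whether the model is fitted to both arms together or within an arm.

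The same section says "we will not conduct inferential statistical analyses". The only between-group comparisons specified elsewhere are for attendance and retention (Feasibility and Acceptability Measures, and Table 3).

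**The concern.** A one-way repeated measures ANOVA has one within-person factor, here visit. Its R² is the share of variation that lies between visits. Fitted to both arms together, it measures average change whatever its cause. Fitted to .b alone, it measures change in .b and ignores the control arm.

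The control condition exists to remove change due to the instructor, the peer group, new material, attention and the passage of time. An R² without an arm term puts that change back and calls it an effect of the intervention. The statistic can then be sizeable when .b adds nothing over the control, or near its floor when .b does add something. What is at stake is the meaning of the only effect-size estimate the plan promises for its outcome measures.

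**Working it through.** **The plan's own figure.** Sample Size for Pilot RCT gives 80% power for an effect of 0.74 with 60 completers. Significance level and sidedness are not stated; I assume 5%, two-sided.

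- Two arms of 30: (1.960 + 0.842) × √(2/30) = 0.72 by the normal approximation; the exact t-test calculation gives 0.736. Power at 0.74 is 80.5%.
- One group of 60, within person: 2.802/√60 = 0.36; the exact calculation gives 0.368.

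So 0.74 is a between-arm effect. The sample-size statement presupposes an arm contrast that the named analysis does not supply.

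**What the R² responds to.** The documents give no value for R², so this is an illustration. Assumptions: SD 1, k = 4 visits, equal correlation ρ = 0.5 between visits, and a step change after baseline that is then held, of size b in .b and c in control. Take partial R² = SS(time)/(SS(time) + SS(residual)). Per person, in expectation for large samples:

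- time: T = ((b + c)/2)² × (k − 1)/k
- arm-by-visit, which falls into the residual of the pooled model: I = ((b − c)/2)² × (k − 1)/k
- residual: V = (1 − ρ)(k − 1) = 1.5
- pooled partial R² = T/(T + I + V)

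Putting numbers in:

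- b = c = 0.25: T = 0.0469, I = 0; R² = 0.0469/1.5469 = 0.030
- b = 0.5, c = 0: T = 0.0469, I = 0.0469; R² = 0.0469/1.5938 = 0.029
- b = c = 0.5: T = 0.1875, I = 0; R² = 0.1875/1.6875 = 0.111
- b = 0.25, c = −0.25: T = 0; R² = 0

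At finite size the sample value is larger. With no change in either arm it averages about 1/60 = 0.017.

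**Simulation** (4,000 replicates per setting, 30 per arm, ρ = 0.5):

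| Change in .b / control (SD) | True arm effect | SS(time)/SS(total), pooled | Partial R², pooled |
|---|---|---|---|
| 0.5 / 0.5 | 0 | 0.051 | 0.123 |
| 0.25 / 0.25 | 0 | 0.018 | 0.047 |
| 0.5 / 0 | 0.5 | 0.017 | 0.045 |
| 0.25 / −0.25 | 0.5 | 0.006 | 0.016 |
| 0 / 0 | 0 | 0.006 | 0.017 |

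The largest R² occurs with no arm effect, and a true effect of 0.5 SD can give the same R² as no change at all.

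- At 22 per arm (Table 3 accepts "At least 50% retained at 3 and 6-mo"; 50% of 45 is 22.5), the 0.25/0.25 and 0.5/0 rows give 0.021 vs 0.019, partial 0.052 vs 0.050.
- At ρ = 0.3 (30 per arm) they give 0.021 vs 0.020, partial 0.038 vs 0.037. At ρ = 0.7 they give 0.016 vs 0.015, partial 0.065 vs 0.062.
- With three visits (ρ = 0.5) they give 0.019 vs 0.019, partial 0.055 vs 0.053. Three is included because Recruitment and Baseline and Follow-up Survey Data stop at 3 months.

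**Fitted in .b alone.** With b = 0.5 the partial R² is 0.14 whether the control arm improves by 0.5 SD or not at all.

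**The contrast the design supports.** In the same simulated data the baseline-adjusted difference at the last visit averages 0.00 SD for 0.25/0.25 and 0.50 SD for 0.5/0.

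**The case against.** **Arm may have been meant as the one factor.** The wording about effects of the intervention, the two-group design and the 0.74 all fit that reading. This stands as a possibility. The model would then be misnamed, and the sentence would still need correcting because it does not mention arm.

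**The illustration coincides by construction.** This is true: both headline scenarios have a mean change of 0.25 SD over the two arms, so their pooled R² must be close, and varying the correlation or the number of visits adds little. They show that the statistic cannot tell the two situations apart; they do not predict the size of a distortion in this trial. The .b-only result shows that the mechanism does not depend on pooling.

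**The model might be fitted in each arm and the two R² compared.** That would separate the scenarios: partial R² is about 0.06 in each arm when both improve by 0.25 SD, and 0.14 against 0.03 when only .b improves by 0.5 SD. The plan does not say this, however, and two R² side by side are still not an estimate of the difference between arms.

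**The outcomes are exploratory and no inference is planned.** The first part limits the consequence. The second does not answer the point, which concerns what is estimated and not whether it is tested.

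**Conclusion.** The concern holds. As worded, the plan reports change over visits as an effect of the intervention, and no other section supplies a between-arm analysis of the outcome scales. That conclusion rests on the standard meaning of the named model. The R² values rest on the assumed correlation, trajectories and sample sizes, and they only illustrate the mechanism.

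The point should be fixed but does not threaten the trial's main purpose. The Table 3 feasibility conclusions are unaffected, and Aim 3b concerns whether the measures are feasible. General Information says the pilot results will inform the size of the full trial, but no section says this R² will be used for that.

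**What to change.** Replace the effect-size sentence with, for example:

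> *For each outcome, means and SDs will be given by arm at each visit. At each follow-up visit we will report the estimated difference between .b and attention control, adjusted for baseline, with the outcome SD, from a repeated measures model with arm, visit and arm-by-visit terms that allows for correlation within person, in youth analysed as randomised.*

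The difference in mean change between arms, with its SD, is a simpler alternative. Any R² for time that is kept should be defined, labelled as change over time, and not attributed to the intervention. The number of visits should be settled in the same edit.

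Three related points can be dealt with at the same time:

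- State whether randomised youth who attended no lesson are included. Enrollment and Data Collection Procedures says "enrollment will be defined as completing consent, baseline survey, and at least one lesson of the intervention or control condition", and lessons come after group assignment.
- State how missing follow-up is handled, given the retention that Table 3 accepts.
- If a 95% interval is reported, change the statement that no inferential analyses will be done to one that no hypothesis tests will be done. Also state how the six delivery cohorts are handled, or that the interval ignores them.

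The cost is a short paragraph and no new data. An interval, if given, will be wide. The half-width is about t × √((2/n)(1 − ρ²)): at ρ = 0.5, 2.00 × √(0.0667 × 0.75) = ±0.45 SD at 30 per arm and 2.02 × √(0.0909 × 0.75) = ±0.53 SD at 22 per arm. Clustering by cohort multiplies this by √(1 + (m − 1) × ICC), with m = 10 or 7.3 youth per cohort. For an assumed ICC of 0.01 to 0.10 the result is ±0.47 to ±0.62 SD at 30 per arm and ±0.55 to ±0.68 SD at 22 per arm, before allowing for there being only six cohorts.
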